**Original Release: May 11, 2017**

**Current Version: Mar 1, 2018**

## Revision History

Revision Number	Release Date	Template number and version	Section	Change	Reason for Change
AA	May 11, 2017	90702637 Rev./Ver. AH	N/A	N/A	Initial release
AB	Jul 24, 2017	90702637 Rev./Ver. AH	Whole document	Delete requirement for magnet and LV lead delivery system, and related description and assessment.	Regulatory requirement.
AB	Jul 24, 2017	90702637 Rev./Ver. AH	Whole document	Delete non-Gore coating leads.	Regulatory requirement.
AB	Jul 24, 2017	90702637 Rev./Ver.	Whole document	Delete the assessment of Beeper function.	Regulatory and trial

Revision Number	Release Date	Template number and version	Section	Change	Reason for Change
		AH			management requests.
AB	Jul 24, 2017	90702637 Rev./Ver. AH	Table 12-3	Parameters for RV shock impedance tests added.	Protocol refinement
AC	Mar 1, 2018	90702637 Rev./Ver. AI	Contact Information	author information deleted	Based on protocol template
AC	Mar 1, 2018	90702637 Rev./Ver. AI	5.1, 6.1, 10.3, 12, 20.3	Descriptions regarding no pacing function during MRI protection mode deleted, and description on synchronization pacing added. Item 4 and 5 from exclusion criteria dropped. Requirement for 12 lead ECG and 10s ECG episode cancelled. Sections for subject evaluation before MRI and MRI visit updated.	The function of pacing under MRI protection mode was added for the device.
AC	Mar 1, 2018	90702637 Rev./Ver. AI	12.7.1.1	Lift the requirement for magnet origin.	Based on magnet availability in hospitals
AC	Mar 1, 2018	90702637 Rev./Ver. AI	12.1, 12.4	Add: A pregnancy test must be performed within 7 days prior to the index procedure in women of child-bearing potential	Trial management request

## **2. Protocol Synopsis**

Observation of ImageReady™ MR Conditional Defibrillation System in China (MR ICD)																	
Study Objectives	To observe the safety and effectiveness of ImageReady™ MR conditional defibrillation system in a Chinese population.																
Test Device	ImageReady™ MR Conditional Defibrillation System																
Device Type	
Pulse Generator
 

DYNAGEN ICD	D150, D152	

DYNAGEN CRT-D	G158	

INOGEN ICD	D140, D142	

INOGEN CRT-D	G148	

 
Defibrillation Lead (active fixation)
 

RELIANCE 4-FRONT (single coil, Gorecoating)	0692, 0693, 0657	

RELIANCE 4-FRONT (dual coil, Gore coating)	0695, 0696, 0658	

 
LV Lead
 

ACUITY X4 (straight)	4671, 4672	

ACUITY X4 (spiral)	4674, 4675, 4677, 4678	

 
DYNAGEN series pulse generators will be used in this study, including 10 ICDs (with at least 2 single chamber and 2 dual chamber ICDs) and 10 CRT-Ds.
 
Lead selection will be mainly decided according to clinical requirement.
	DYNAGEN ICD	D150, D152	DYNAGEN CRT-D	G158	INOGEN ICD	D140, D142	INOGEN CRT-D	G148	RELIANCE 4-FRONT (single coil, Gorecoating)	0692, 0693, 0657	RELIANCE 4-FRONT (dual coil, Gore coating)	0695, 0696, 0658	ACUITY X4 (straight)	4671, 4672	ACUITY X4 (spiral)	4674, 4675, 4677, 4678
DYNAGEN ICD	D150, D152																
DYNAGEN CRT-D	G158																
INOGEN ICD	D140, D142																
INOGEN CRT-D	G148																
RELIANCE 4-FRONT (single coil, Gorecoating)	0692, 0693, 0657																
RELIANCE 4-FRONT (dual coil, Gore coating)	0695, 0696, 0658																
ACUITY X4 (straight)	4671, 4672																
ACUITY X4 (spiral)	4674, 4675, 4677, 4678																
Study Design	Multi-center, prospective, single –arm study																
Planned Number of Subjects	20																
Planned	approximately 5 investigational sites from China																

Observation of ImageReady™ MR Conditional Defibrillation System in China (MR ICD)	
Number of Investigational Sites	
Primary Safety Endpoint	MR scan-related Complication-free rate between the MR Scan and the MRI + 1 Month Visit
Primary Effectiveness Endpoints	

1. Abnormal increase in RV shocking impedance from the pre-MR scan to the 1 Month post-MR scan

2. Increase in RV pacing threshold from the pre-MR scan to the 1 Month post-MR scan

3. Decrease in RV sensed amplitude from the pre-MR scan to the 1 Month post-MR scan

4. Increase in LV pacing threshold from the pre-MR scan to the 1 Month post-MR scan

5. Decrease in LV sensed amplitude from the pre-MR scan to the 1 Month post- MR scan

Ancillary Assessments	

1. Assessment of RV and LV impedances

2. Assessment of RA lead measurements

3. Assessment of VT/VF episodes post-MR-scan

4. Assessment of programming the MRI Protection Mode

5. Assessment of Image Artifacts for non-medically necessary MR scans.

Follow-up Schedule	
Phase I is completed when all the subjects finish MRI + 1 Month Visit, which starts Phase II till 1 year post implantation.
 

- Screening and Enrollment Visit (<math>\leq</math> 30 days prior to implant procedure )

- Implant Procedure

- Pre-Discharge Clinic Visit (3 – 72 hours post-implant)

- MRI Visit (6-9 weeks post-implant)

Observation of ImageReady™ MR Conditional Defibrillation System in China (MR ICD)	
	

- MRI + 1 Month Visit (<math>30 \pm 7</math> days post-MRI Visit)

- Every Three-month follow-ups post MR scan (<math>\pm 14</math> days, recommended)

- One Year Visit (<math>365 \pm 45</math> days post-implant)

Study Duration	Phase I is expected to last about 9 months after first subject enrollment, by when all the subjects will have finished MRI +1 Month Visit. Phase II continues to all the subjects complete one year follow-up post-implant, and the whole study is expected to last about 20 months after first subject enrollment.
Key Inclusion Criteria	

1. Subject is indicated to Class I/II indications per guidelines/consensus released by Chinese Society of Cardiac Pacing and Electrophysiology

2. Subject must have the ImageReady System as their initial (de novo) defibrillation system implant

3. Subject will receive an ICD or CRT-D pulse generator in the left or right pectoral region ICD

4. Subject is able and willing to undergo an MR scan

5. Subject is willing and capable of providing informed consent and participating in all testing/ visits associated with this clinical study at an approved clinical study center and at the intervals defined by this protocol

6. Subject is age 18 or above

Key Exclusion Criteria	

1. Subject has other active or abandoned implanted cardiac rhythm devices, components or accessories present such as pulse generators, leads, lead adaptors or extenders

2. Presence of metallic objects that represent a contraindication to MR imaging at the discretion of the Radiologist and impacting the ability to conduct the study protocol

3. Subject needs or will need a medically necessary MR scan, before completing the 1-month post-MR follow-up visit

4. Subject is not clinically capable of tolerating the absence of Tachycardia therapy support for the duration that the pulse generator is in MRI Protection Mode, per Physician discretion

Observation of ImageReady™ MR Conditional Defibrillation System in China (MR ICD)	
	

5. Subjects currently requiring dialysis

6. Subject has a mechanical heart valve

7. Subject has a known or suspected sensitivity to dexamethasone acetate (DXA)

8. Subject is currently on the active heart transplant list

9. Subject has documented life expectancy of less than 12 months

10. Subject is enrolled in any other concurrent study that might interfere with this study

11. Women of childbearing potential who are or might be pregnant at the time of this study

Statistical Methods	
Primary Statistical Hypothesis	This study is a single-arm, small sample clinical study without any hypothesis testing. It can be considered reasonable if up to 2 failed cases of primary safety endpoint event occur. It can be considered reasonable if up to 2 failed cases of endpoint event occur in each of the five primary effectiveness endpoints.
Statistical Test Method	Descriptive statistics will be conducted for the endpoint events.
Sample Size Parameters	This study is a single-arm, small sample clinical study without any hypothesis testing. Twenty subjects (10 with ICD and 10 with CRT-D) will be enrolled. It is assumed that the attrition should not be more than 2 cases in each group, so that at least 8 subjects shall be included in the final analysis for each group.

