#### **11.4. Enrollment Controls**

According to the study protocol, 10 ICD subjects (at least 2 single chamber ICDs and 2 dual chamber ICDs) and 10 CRT-D subjects will be enrolled. It should be ensured that at least 8 ICD subjects (at least 1 single chamber ICD and 1 dual chamber ICD) and 8 CRT-D subjects undergo protocol required MR scan and complete all the sequences. It should be ensured that both single coil and dual coil defibrillation leads are implanted. It should be ensured that both straight and spiral LV leads are implanted. Subject enrollment might be expanded to meet the above requirement to support product registration.

Generally, one individual center may not enroll more than 10 subjects. Investigational sites will be notified when the enrollment goal is close to being reached and once enrollment is complete.

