### **13.1.6. Primary Effectiveness Endpoint 5: Pre-MR scan vs. 1 Month Post-MR Scan LV Sensed Amplitude**

Subjects will be considered a success if the average sensed amplitude at the MRI + 1 Month Visit remains  $\geq 5.0$  mV and above 50% of the pre-MR scan value, otherwise, it is a primary effectiveness endpoint 5 event.

The performance goal of this endpoint for the ENABLE MRI study was 85%. There is no hypothesis testing in the MR ICD study, and it can be considered reasonable if up to 2 failed cases of primary effectiveness endpoint 5 occur.

The data set for the primary effectiveness endpoint 5 will only include subjects who undergo the study-required MR scan and complete all the sequences, and will not include subjects that meet any of the following exclusions:

- Has a medically necessary scan between implant and the MRI + 1 Month Visit
- Fails to meet labeled MRI Conditions of Use
- Experiences a lead-related complication between MRI Visit and the MRI + 1 Month Visit
- Average LV sensed amplitude <5mV pre-MR scan

The time window for MRI + 1 Month visit is  $30\pm 7$  days post MR scan, so it will capture events within at least 23 days post scan. In this small sample size study, missing data will be excluded.

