### **13.3. Sample Size**

The MR ICD study is a small sample size study without any formal hypothesis testing. Twenty subjects (10 with ICD and 10 with CRT-D) will be enrolled. It is assumed that the attrition should not be more than 2 cases in each group, so that at least 8 ICD subjects (at least 1 single chamber and 1 dual chamber ICD) and 8 CRT-D subjects shall undergo required MR scan and complete all the sequences. Sample size might be expanded to meet this assumption.

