#### **13.4.3. Data Set, Subgroups and Missing Data**

The data set for the safety endpoint will include all subjects who undergo the study-required MR scan sequences (scan sequences initiated, whether complete or not). The data set for the effectiveness endpoint will only include subjects who undergo the study-required MR scan and complete all the sequences, and will not include subjects that meet any of the following exclusions:

- Has a medically necessary scan between implant and the MRI + 1 Month Visit
- Fails to meet labeled MRI Conditions of Use

- Experiences a lead-related complication between MRI Visit and the MRI + 1 Month Visit MRI

Subjects whose average RV sensed amplitude <5mV pre-MR scan will also be excluded for primary effectiveness endpoint 3 assessment, and subjects whose average LV sensed amplitude <5mV pre-MR scan will also be excluded for primary effectiveness endpoint 5 assessment.

There is no formal subgroup analysis in the MR ICD study, however, descriptions may be grouped on study site, subject sex, device type (single chamber ICD, dual chamber ICD and CRT-D), etc.

The primary endpoints for the MR ICD study are comparisons between MRI Visit and the MRI + 1 Month Visit, absence of either comparator will be missing data for that endpoint. Missing data will be excluded for endpoint assessment in this small sample size MR ICD study.

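### The synopsis counts 8 subjects per group in the final analysis, but the enrolment rule secures only 8 who complete the scan, before the effectiveness exclusions apply.

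*Combined protocol and SAP*

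**What the plan says.** The synopsis (Sample Size Parameters) states "Twenty subjects (10 with ICD and 10 with CRT-D) will be enrolled". It continues "It is assumed that the attrition should not be more than 2 cases in each group", and from this concludes that "at least 8 subjects shall be included in the final analysis for each group".

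The body starts from the same attrition assumption and ends at an earlier stage. Protocol section 13.3 requires at least 8 ICD subjects and "8 CRT-D subjects shall undergo required MR scan and complete all the sequences"; SAP section 3.5 repeats this. Section 11.4 sets the matching enrolment control, at least 8 ICD and "8 CRT-D subjects undergo protocol required MR scan and complete all the sequences", and adds "Subject enrollment might be expanded to meet the above requirement to support product registration".

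For the effectiveness endpoints, completing all sequences is only the entry condition. Sections 13.1.2 to 13.1.6 and 13.4.3 then remove subjects who have a medically necessary scan between implant and the 1-month visit, who fail the labelled Conditions of Use, or who have a lead-related complication between the two visits. Endpoint 3 also removes subjects with a low pre-scan RV amplitude, and endpoint 5 has the parallel LV rule: "Average LV sensed amplitude <5mV pre-MR scan". Finally, "Missing data will be excluded for endpoint assessment in this small sample size MR ICD study".

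**The concern.** The same number 8 is attached to two different stages of follow-up. The allowance of 2 per group may be used up by the time of scan completion, which leaves nothing for later exclusions or a missed 1-month visit. The expansion clause in section 11.4 does not close the gap, because it is tied to scan completion and to the device and lead mix, not to evaluable subjects.

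The consequence is greatest for endpoints 4 and 5. ICD subjects have no LV lead to test, so the CRT-D completers are the whole denominator, and endpoint 5 has the extra 5 mV exclusion. The plan regards up to 2 failures per endpoint as reasonable whatever the denominator, so a reader who takes 8 from the synopsis may read that allowance against a larger number than is analysed.

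**Working it through.** **The plan's own figure.** 10 enrolled − 2 lost = 8 per group, or 16 in total. The subtraction is correct; what differs is the stage at which the 8 are counted.

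| Place | What the 8 per group are |
|---|---|
| Synopsis | subjects in the final analysis |
| Protocol 11.4 | subjects completing all sequences |
| Protocol 13.3 and SAP 3.5 | subjects completing all sequences |
| Protocol 13.1.2–13.1.6 and 13.4.3 | completers, less exclusions and missing data |

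With exactly 8 completers in a group, one later exclusion or one missing 1-month measurement leaves 8 − 1 = 7. This step needs no assumption.

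**Size of the gap.** The documents give no rate of loss after scan completion. Let q be the assumed chance that a completer is later excluded or has missing data, independently of the others, with q from 5% to 30%. For one group:

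- expected evaluable from 8 completers: 8(1 − q)
- chance that all 8 remain evaluable: (1 − q)^8
- chance of at least 8 evaluable if all 10 complete: the binomial probability of 8 or more out of 10 with success probability 1 − q

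| Assumed q | Expected evaluable of 8 | P(all 8 of 8) | P(at least 8 of 10) |
|---|---|---|---|
| 5% | 7.6 | 0.663 | 0.988 |
| 10% | 7.2 | 0.430 | 0.930 |
| 20% | 6.4 | 0.168 | 0.678 |
| 30% | 5.6 | 0.058 | 0.383 |

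The third column describes the floor that the enrolment rule permits; the last describes the plan going as intended.

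**Denominators by endpoint.** Endpoints 1–3 draw on both groups: 20 planned and at least 8 + 8 = 16 completers. Endpoints 4–5 draw on CRT-D subjects only: 10 planned and at least 8 completers. Endpoints 3 and 5 are reduced further by the 5 mV rule. Any expansion of enrolment would raise these counts.

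**What two failures mean.** The observed success proportion is (n − 2)/n:

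- n = 20: 18/20 = 90%
- n = 16: 14/16 = 87.5%
- n = 8: 6/8 = 75% (exact 95% CI 34.9% to 96.8%)
- n = 6: 4/6 = 67% (exact 95% CI 22.3% to 95.7%)

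For the LV endpoints, the part due to a shortfall from 8 to 6 is the step from 75% to 67%. The low value at n = 8 comes from the fixed allowance itself, which is a separate matter.

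**Safety.** Protocol sections 13.1.1 and 13.4.3 include everyone whose scan was initiated and do not apply the effectiveness exclusions. In that set, only missing data could take a group of 8 completers below 8.

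**The case against.** The strongest case on the other side is that this is a loose synopsis sentence in a study with no hypothesis test and no power target, so no inferential result depends on the number 8. The sentence rests on a stated assumption and does not define the final analysis. Several losses are partly pre-empted: an expected medically necessary scan before the 1-month visit is itself an exclusion criterion (section 10.3, item 3), and the Conditions of Use must be confirmed before scanning (section 12.7.2.1). The 20% and 30% rates have no support in the documents. All of this stands, and it limits the weight of the point. None of it reconciles the synopsis with sections 11.4 and 13.3 and SAP 3.5.

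A reader might infer more than the documents support:

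- *That the sample-size arithmetic is wrong.* It is not: 10 − 2 = 8, and the 20 enrolled and the 8 completers per group are also stated.
- *That the study will fall short.* The plan is 10 per group. If all complete, at least 8 evaluable remains likely at the lower assumed loss rates.
- *That every primary endpoint is affected in the same way.* The protocol safety set escapes the exclusions. SAP 5.1.2 does also present safety on the Implant population, which carries them, but it presents the Intent population as well. Endpoints 1–3 pool both groups and start from at least 16 completers.
- *That the reporting must change.* SAP 5.1.1, 5.1.2 and 7.5 already plan counts, percentages and exact 95% intervals.

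**Conclusion.** The point holds as an inconsistency between the synopsis and the body. The synopsis states at least 8 analysed per group, while the design secures only 8 scan completers per group, from which the five effectiveness analyses may lose subjects. That conclusion follows from the text alone.

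Its size depends on the later-loss rate, which is assumed here to be 5% to 30%, equal across subjects and independent. The chance of at least 8 evaluable in a group runs from 66% to 6% at the floor of 8 completers, and from 99% to 38% if all 10 complete. The minimum is therefore not secured, though it may well be met. The practical effect is largest for LV endpoints 4 and 5.

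**What to change.** Restate the synopsis sentence as at least 8 subjects per group completing all scan sequences, in line with section 13.3 and SAP 3.5, which can keep their wording on this. Add that the evaluable number for each effectiveness endpoint may be lower because of the exclusions and missing data, and give the starting numbers:

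- endpoints 1–3: both groups, 20 planned, at least 16 completers
- endpoints 4–5: CRT-D subjects only, 10 planned, at least 8 completers
- endpoints 3 and 5: further reduced by the 5 mV rule
- all subject to any expansion of enrolment

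The planned exact confidence intervals need no change. The cost is wording, plus a stated analysed number that looks less favourable. Actually securing 8 evaluable subjects per group would mean tying the expansion clause to evaluable counts. That is a larger design change and is not needed to remove the contradiction.

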#### **4. Introduction**

Magnetic resonance imaging (MRI) is a diagnostic technique that images body parts by producing a static magnetic field followed by rapidly changing radiofrequency fields to excite hydrogen nuclei. MRI scanning is now the imaging modality of choice for many neurological and musculoskeletal conditions. In the past, implanted cardiac devices including pacemakers and implanted cardioverter-defibrillators (ICD) have been contraindicated in MRI scanners. The potential adverse effects of MRI on defibrillation system include loss of capture due to lead tip heating and cardiac arrhythmias induced by unexpected pacing.

A number of studies have reported on the relative safety of scanning patients with non-MR conditional cardiac pacemakers or implantable cardioverter-defibrillators. Nazarian et. al. reported on 438 patients (54% with pacemakers and 46% with ICDs) undergoing 555 scans (18% involving thorax). In 3 patients, the device reverted to a transient back-up programming mode without long-term effects. The observed changes in sensing, impedance and pacing threshold did not require device revision or reprogramming. Recently, the result of MagnaSafe registry was published. Patients in the registry were referred for clinically indicated nonthoracic (75% with brain or spinal cord) MRI at a field strength of 1.5 T (1000 pacemaker and 500 ICD scans). No deaths, lead failures, losses of capture, or ventricular arrhythmias occurred during MRI. One ICD generator could not be interrogated after MRI; the device had not been appropriately programmed per protocol before the MRI. The ratio of pacing threshold increase  $\geq 0.5$  V, P-wave amplitude decrease  $\geq 50\%$  and R-wave amplitude decrease  $\geq 50\%$  immediately after scan in ICD group was 0.8%, 0.3%, and 0.2%, respectively; and the long-term ratio was 0.3%, 0, 0.

Presently some ICD manufacturers are developing and producing MR conditional defibrillation systems. DYNAGEN and INOGEN, the new generation of defibrillation system series from Boston Scientific (BSC) were designed to be MR conditional.

DYNAGEN and INOGEN defibrillation system series products (pulse generators and leads) have already been approved in China without MR conditional label. BSC China intends to expand the indication with additional MR conditional label, and name the defibrillation system as ImageReady™ MR conditional defibrillation system.

BSCL is conducting a global multi-center study, ENABLE MRI (NCT02652481), on MR conditional systems including DYNAGEN and INOGEN. The study will enroll 500 subjects, to confirm the safety and effectiveness of the ImageReady™ MR Conditional Defibrillation System when used in the 1.5T MRI environment under the labeled Conditions of Use. MR ICD protocol is based on ENABLE MRI study.

China Food and Drug Administration (CFDA) requires certain clinical trial in China to support the approval of ImageReady™ MR conditional defibrillation system.

## **5. Device Description**

The ImageReady MR Conditional Defibrillation System included in the MR ICD Clinical Study, here to forward referred to as the ImageReady System, consists of DYNAGEN and INOGEN series pulse generators, RELIANCE 4-FRONT series defibrillation leads, ACUITY X4 series left ventricle (LV) leads, and INGEVITY series pacing leads for right atrium (RA). See Table 5-1.

**Table 5-1 ImageReady MR Conditional Defibrillation System Components**

Component	Name	Model	Features
Pulse Generators	DYNAGEN	D150	Single chamber ICD, DF4
		D152	Dual chamber ICD, DF4
		G158	CRT-D, DF4, IS4
	INOGEN	D140	Single chamber ICD, DF4
		D142	Dual chamber ICD, DF4
		G148	CRT-D, DF4, IS4
Defibrillation Leads	RELIANCE 4-FRONT active fixation, single coil, Gore coating	0692	59cm
		0693	64cm
		0657	70cm
	RELIANCE 4-FRONT active fixation, dual coil, Gore coating	0695	59cm
		0696	64cm
		0658	70cm
LV leads	ACUITY X4 straight	4671	86cm
		4672	95cm
	ACUITY X4 spiral S	4674	86cm
		4675	95cm

	ACUITY X4 spiral L	4677	86cm
		4678	95cm
RA leads	INGEVITY passive fixation, J type	7735	45cm
		7736	52cm
	INGEVITY active fixation, straight	7740	45cm
		7741	52cm
		7742	59cm
	INGEVITY passive fixation, straight	7731	52cm
		7732	59cm

DYNAGEN and INOGEN pulse generators, belonging to the new generation products of Galaxy, include single chamber ICD, dual chamber ICD and CRT-D, all capable of providing defibrillation therapy. DYNAGEN and INOGEN pulse generators have the same hardware, while DYNAGEN is more advanced product with additional software functions such as ApneaScan, Wireless ECG and RhythmMatch.

The pulse generators and leads listed in MR ICD study protocol have been approved by CFDA with non-MR conditional label. INGEVITY MRI series leads have been approved by CFDA with MR conditional label.

The design of the DYNAGEN and INOGEN pulse generators has minimized the use of ferromagnetic materials which can interact with the fields generated in a typical MRI scan; the circuits have been designed to tolerate voltages that may be induced during scans; and the lead wire has been designed for use with the ImageReady pulse generators specifically to reduce absorption of energy from MRI fields, thus minimizing heating.

DYNAGEN will be used as the only pulse generator in MR ICD study, while lead selection will be decided mainly by investigators based on subjects' anatomy and clinical practice. BSC intends to label the ImageReady MR Conditional Defibrillation System models "MR Conditional" as defined by the American Society for Testing and Materials (ASTM), when used as a system and in accordance with labeled Conditions of Use.

